A by-subject listing for dose omission will be presented for all treated subjects. This listing will include all reported omissions per CRF, regardless of whether the subject had a computed omission based on the actual dosing dates.

- **Dose Interruption**

The number and percentage of subjects with any interruption in their elotuzumab infusion, with 1, 2, 3, or \geq 4 interruptions, with an interruption due to “infusion reaction”, “infusion administration issues” and “other” will be presented. In addition, duration of interruptions (in minutes) will be summarized via descriptive statistics.

A by-subject listing will be generated for elotuzumab IV interruptions. This listing will include reason for interruption, whether the infusion was resumed, and duration of the interruption.

- **IV Rate Reduction**

The number and percentage of subjects with any elotuzumab IV rate reduction, with 1, 2, 3, or \geq 4 rate reductions, and with rate reductions due to “infusion reaction,” “infusion administration issues,” and “other” will be presented.

A by-subject listing will be generated for elotuzumab IV rate reductions.

Lenalidomide:

- **Dose Reduction**

Reduction of Lenalidomide will be computed based on the actual dose received. In any study day (excluding, cycle 1, day 1), the drug will have a calculated reduction compared to the previous day, if the actual level of the administered dose is below the actual level of the administered dose in the previous instance. The information for this analysis will be derived programmatically, using the total daily dose on the “Record of Study Medication - lenalidomide” eCRF page.

The daily dose levels are defined as follows:

- Dose level 0 or full dose (25 mg): \geq 20.0
- Dose level -1 (15 mg): 12.5 mg to < 20.0

- Dose level -2 or starting dose for moderate renal impairment (10 mg): 8.75 to < 12.5 mg
- Dose level -3 for subjects with severe renal impairment (15 mg every 48 hours): 6.25 to < 8.75 mg
- Dose level -4 for subjects with End Stage Renal Disease (ESRD) (5 mg): < 6.25 mg

The number and percentage of subjects with a dose reduction, and the lowest dose level achieved per subject (-1, -2, -3, \leq -4), will be presented by treatment group. This table will be broken out by whether the subject started at the standard dose level or at the 10 mg dose level.

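### SAP 7.4.1.2 builds the lenalidomide level -3 band on a 48-hour average (7.5 mg/day) but applies it to the actual daily dose, so 15 mg every 48 hours is graded level -1

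*SAP*

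**What the plan says.** SAP 7.4.1.2 (Dose Modifications, Lenalidomide) fixes the input first: "Reduction of Lenalidomide will be computed based on the actual dose received". A reduction exists on a study day "if the actual level of the administered dose is below the actual level of the administered dose in the previous instance". The level is "derived programmatically, using the total daily dose on the" lenalidomide study-medication eCRF page.

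The bands follow under the introduction "The daily dose levels are defined as follows":

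- Level 0 (25 mg): 20.0 mg or more.
- Level -1: "Dose level -1 (15 mg): 12.5 mg to < 20.0".
- Level -2 (10 mg): 8.75 to below 12.5 mg.
- Level -3: "Dose level -3 for subjects with severe renal impairment (15 mg every 48 hours): 6.25 to < 8.75 mg".
- Level -4 (5 mg): below 6.25 mg.

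The planned table gives, by treatment group and split by starting dose, the subjects with a reduction and the lowest level each one reached. Reasons are tabulated for calculated reductions. SAP 8.7 names the reduction summary as a topline output.

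The regimen can occur on study, because Protocol Table 4.3.4.3-3 gives 15 mg every 48 hours for severe renal impairment without dialysis. SAP 7.4.1.2 states no conversion of that regimen to a daily equivalent.

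**The concern.** The level -3 band and the variable it is applied to are on different scales. The band describes an average over two days. The rule reads the amount taken on one day. On a dosing day of the 48-hour regimen that amount is 15 mg, the same as for a subject taking 15 mg every day at twice the average dose.

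The stake is the accuracy of one descriptive exposure table. The subjects for whom level -3 was created would not be counted in it. Some real falls in average dose would go uncounted, along with their reasons, and one rise in average dose would be counted as a reduction. The interruption table does not clearly fill the gap: it asks for two or more days without drug, and this regimen leaves one drug-free day between doses.

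**Working it through.** **Inputs**

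- Bands and derivation rule: SAP 7.4.1.2.
- Regimen of 15 mg every 48 hours: Protocol Table 4.3.4.3-3.
- Capsule strengths 5, 10, 15 and 25 mg: Protocol Table 4.1-1.
- Capsules are swallowed whole: Protocol 4.3.1.
- Dosing on Days 1-21 of a 28-day cycle: Protocol 3.1.

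**Step 1. Reproduce the plan's cut-points.** Take the nominal daily doses 25, 15, 10, 15/2 = 7.5 and 5 mg, and the midpoint of each neighbouring pair:

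- (25 + 15)/2 = 20.0
- (15 + 10)/2 = 12.5
- (10 + 7.5)/2 = 8.75
- (7.5 + 5)/2 = 6.25

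All four match the SAP exactly. The level -3 band therefore rests on the 48-hour average.

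**Step 2. Apply the bands to a single day's dose.** Whole capsules give daily totals in multiples of 5 mg:

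| Daily total (mg) | Level |
|---|---|
| 25 | 0 |
| 20 | 0 |
| 15 | -1 |
| 10 | -2 |
| 5 | -4 |

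No total lies in 6.25 to below 8.75 mg, so level -3 is empty on this reading. If off days were stored as 0 mg and classified, they would be level -4, still not -3. The rule speaks of administered doses, so off days are not naturally included. If they were, every subject's rest days (22-28) would also be level -4.

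**Step 3. Compare the two readings for a change of regimen.** The averaged reading uses 7.5 mg/day for 15 mg every 48 hours (q48h).

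| Change | Literal rule | Averaged dose |
|---|---|---|
| 25 mg daily to 15 mg q48h | 0 to -1, reduction | 0 to -3, reduction |
| 15 mg daily to 15 mg q48h | -1 to -1, none | -1 to -3, reduction |
| 10 mg daily to 15 mg q48h | -2 to -1, none | -2 to -3, reduction |
| 15 mg q48h to 10 mg daily | -1 to -2, reduction | -3 to -2, none |
| 15 mg q48h to 5 mg daily | -1 to -4, reduction | -3 to -4, reduction |

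Row 1 is counted as a reduction either way, but with lowest level -1 instead of -3. Rows 2 and 3 are missed reductions. In row 3 the lowest level is -2 instead of -3. Row 4 is a false reduction, since the average dose rises from 7.5 to 10 mg/day. In row 5 the lowest level is -4 on both readings.

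**Step 4. Check the averaging window.** Alternate-day dosing on Days 1, 3, ..., 21 is 11 doses, or 11 × 15 = 165 mg.

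- Over the 48-hour interval: 15/2 = 7.5 mg/day, level -3.
- Over Days 1-21: 165/21 = 7.86 mg/day, level -3.
- Over the 28-day cycle: 165/28 = 5.89 mg/day, level -4.

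An instruction to average without a stated window could therefore replace one misclassification with another.

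**The case against.** The best case for the plan is that its intent is plain. The cut-points are correct, the author had already converted the regimen to 7.5 mg/day, and the regimen is named beside its band. A programmer who sees that label knows where the regimen belongs. This stands as a statement of intent, but the written derivation does not carry it out.

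The eCRF page is also not in the documents. If it stores a 7.5 mg daily equivalent, level -3 is assigned correctly. A reader might infer that level -3 can never be assigned. The documents do not support that as an absolute. They support it only for a literal per-day reading, which the reference to the actual dose received makes the likelier one.

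Three further inferences go too far:

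- *The cut-points are an arithmetic error.* They are exact midpoints. The fault is the mismatch with the variable.
- *Every subject on the regimen is misreported.* A subject who also reaches 5 mg has lowest level -4 on both readings. A subject already counted for another reduction stays in the reduction count.
- *The table would show a dose increase after 10 mg daily.* It reports reductions and lowest levels, not increases. The effect is a missed reduction and a lowest level of -2 instead of -3.

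Other outputs limit the damage. The by-subject listing keeps all investigator-reported reductions, whether or not calculated. Dose intensity in SAP 7.4.1.3 uses cumulative dose over elapsed time, so it separates the regimens: a full cycle gives 165/4 = 41.25 mg/week for 15 mg every 48 hours, against 21 × 15/4 = 78.75 mg/week for 15 mg daily. These outputs do not correct the reduction table itself.

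**Conclusion.** The point holds as a mismatch between the level -3 band and the variable it is applied to. Followed literally, the rule grades each dosing day of 15 mg every 48 hours as level -1 and leaves level -3 empty. Most such subjects then show a lowest level that is one or two steps too high. Moves to the regimen from 15 mg or 10 mg daily are missed, and a move from it to 10 mg daily is falsely counted.

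This rests on two assumptions: that the eCRF records the dose taken on each dosing day rather than a 7.5 mg equivalent, and that drug-free days are not classified.

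The consequence is small. Protocol 3.3.2 excludes creatinine clearance below 30 mL/min, so the regimen should arise mainly from renal decline on study. The documents give no count of such subjects. Efficacy, type I error and dose intensity are untouched. The correction is worth making because the table is a topline output and the category exists only for this regimen.

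**What to change.** Add a sentence to the lenalidomide reduction rule in SAP 7.4.1.2: records on an every-48-hours schedule are assigned a level from the dose averaged over the 48-hour dosing interval (15/2 = 7.5 mg/day, level -3), and not over the 28-day cycle. The same averaged level should be used when a record is compared with the previous instance.

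The sentence must also say how these records are found. The prescribed regimen or the dose modification page is the better source, if it captures the interval. An alternate-day dosing pattern is the fallback, but it cannot by itself separate this regimen from 15 mg daily with missed days. If the eCRF already stores a daily equivalent, stating that in the SAP is enough.

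The cost is one or two sentences, a small derivation change and a check of what the eCRF collects. The change affects only how recorded doses are classified, not any dosing rule.

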4.3.3 Dose Delay or Interruption

If the dose of one drug in the regimen (ie, lenalidomide, dexamethasone or elotuzumab) is delayed or interrupted, the treatment with the other drugs may continue as scheduled. Subjects experiencing a 28 day delay in all study drugs lenalidomide, dexamethasone, and elotuzumab due to an adverse event(s) related to study treatment must be discontinued from study drug. Subjects experiencing delays unrelated to study therapy, for example due to radiation therapy may delay study treatment up to 42 days. Delays greater than 28 days must be discussed with the medical monitor.

Each cycle is 28 days. While dose delays or interruptions are permitted, the start of each cycle cannot be delayed and is fixed relative to Cycle 1 Day 1. Adjustments to the Cycle 1 Day 1 anchored schedule should not be performed. Missed doses should be skipped, not delayed, if not given within the allowed window.

Subjects may continue on study therapy even if components of the study therapy must be discontinued. For example, a subject on lenalidomide and dexamethasone may continue on study therapy even if dexamethasone must be discontinued for an adverse event. Likewise, a subject on

the investigational arm may continue on study therapy if elotuzumab must be discontinued for an adverse event or other reason. Patients are considered still on study therapy even if they continue solely on lenalidomide.

Please consult the BMS medical monitor or any questions regarding dose interruption or study therapy discontinuation.

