4.3.4.3 Lenalidomide

Dose adjustments, as summarized below, are recommended for the management of NCI CTCAE Grade 3 and 4 toxicities for thrombocytopenia, neutropenia or other toxicities that are judged by the investigator to be related to lenalidomide. Information in Table 4.3.4.3-1 and Table 4.3.4.3-2 is based on current standard of clinical practice.

When Platelet Counts:	Recommended Course

 Fall to $< 30,000/\text{mm}^3$ Return to $\geq 30,000/\text{mm}^3$ 	Interrupt lenalidomide treatment; follow complete blood counts weekly. Resume lenalidomide at 15 mg, Days 1 - 21, once daily.
For each subsequent drop $< 30,000/\text{mm}^3$ Return to $\geq 30,000/\text{mm}^3$	Interrupt lenalidomide treatment. Resume lenalidomide at 5 mg less than previous dose, Days 1 - 21, once daily. Do not dose below 5 mg.

When Neutrophil Counts:	Recommended Course
Fall to $< 1000/\text{mm}^3$ Return to $\geq 1000/\text{mm}^3$ and neutropenia is the only toxicity	Interrupt lenalidomide treatment, add G-CSF; ^a follow complete blood counts weekly. Resume lenalidomide at 25 mg, Days 1 - 21, once daily.
Return to $\geq 1000/\text{mm}^3$ and if other toxicity	Resume lenalidomide at 15 mg, Days 1 - 21, once daily.
For each subsequent drop $< 1000/\text{mm}^3$ Return to $\geq 1000/\text{mm}^3$	Interrupt lenalidomide treatment. Resume lenalidomide at 5 mg less than previous dose, Days 1 - 21, once daily. Do not dose below 5 mg.

In case of neutropenia, consider the use of growth factors in subject management.

^a G-CSF = Granulocyte Colony-Stimulating Factor

Lenalidomide Dose Adjustments in Subjects with Renal Impairment

Since lenalidomide is primarily excreted via the kidney, adjustments to the dose of lenalidomide are provided based on the lenalidomide country prescribing information. The regimen of 21 day dosing every 28 days remains the same despite the dose reductions described below.

Table 4.3.4.3-3: Lenalidomide Dose Adjustments in Subjects with Renal Impairment^a	
Creatinine Clearance (CRCL):	Recommended Course
Moderate renal impairment (30 ≤ CRCL < 60 mL/min)	10 mg, every 24 hours
Severe renal impairment (CRCL < 30 mL/min, not requiring dialysis)	15 mg every 48 hours
End Stage Renal Disease (CRCL < 30 mL/min, requiring dialysis)	5 mg once daily. On dialysis days, dose should be administered following dialysis

^a Source: Lenalidomide USPI

Dose Adjustments During Treatment for Other Grade 3 and 4 Toxicities

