6.2 Treatment Regimens

Subjects will be randomized to one of two treatment arms, E-Ld or Ld. Subjects will receive these treatments in 28-day cycles until disease progression, unacceptable toxicity or withdrawal of consent.

On Arm A (E-Ld) subjects receive:

- Elotuzumab: 10 mg/kg intravenous (IV) on Days 1, 8, 15 and 22 of the cycle during Cycles 1 and 2; Days 1 and 15 during Cycles 3-18; and 20mg/kg intravenous (IV) on Day 1 of the cycle during subsequent cycles.
- Lenalidomide: 25 mg orally (po) on Days 1-21 of each cycle.
- Dexamethasone: Administered on Days 1, 8, 15 and 22 of cycle. 28 mg po + 8 mg IV whenever given prior to elotuzumab; 40 mg po on weeks on which no elotuzumab is given.

On Arm B (Ld) subjects receive:

- Lenalidomide: 25 mg po on Days 1-21 of each cycle.
- Dexamethasone: 40 mg po on Days 1, 8, 15 and 22 of each cycle.

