The reason for dose reduction as reported by the investigator will be tabulated for all instances with a calculated reduction based on the dose modification for Lenalidomide page. A category “unknown” will be defined for all calculated reductions with no reason reported by the investigator.

A by-subject listing of dose reductions will be generated. This will include all reported reductions per investigator, regardless of whether it met the requirements for a calculated reduction.

- **Dose Interruption**

In any cycle, the Lenalidomide dose will be considered as interrupted if there is a gap of two or more days between two dosing dates within that cycle where the subject did not receive the study drug. This will be calculated based on the information from the dose modification CRF for Lenalidomide.

The number and percentage of subjects with dose interruption, with 1, 2, 3, or \geq 4 reported interruptions will be presented. For subjects with a computed interruption, their reason for interruption will be summarized from the dose modification CRF. For subjects without an available reason for interruption, the category “unknown” will be used.

Dexamethasone (IV) and Oral:

For IV dexamethasone the following summaries will be provided:

- The number of subjects with any dose delay, with 1, 2, 3, or \geq 4 reported delays, and with a reason for delay of “hematologic toxicity”, “non-hematologic toxicity”, “AE”, “dosing error” and “other”.
- The number of subjects with any reported dose omission, with 1, 2, 3, or \geq 4 reported omissions, and with a reported reason for omission of “hematologic toxicity”, “non-hematologic toxicity”, “AE”, “dosing error” and “other”.
- The number of subjects who discontinued the study drug, and reason for the discontinuation (hematologic toxicity, non-hematologic toxicity, AE, dosing error, or other).

- The number of subjects with any reduction in the dose of the drug, and with a reason for the reduction of “hematologic toxicity”, “non-hematologic toxicity”, “AE”, “dosing error”, and “other”).

For PO dexamethasone the following summaries will be produced:

- The number of subjects with any dose modification, with 1, 2, 3, or ≥ 4 reported modifications, and with a reason for the modification of “hematologic toxicity”, “non-hematologic toxicity”, “AE”, “dosing error” and “other”).

By subject listings of record of study medication for each of IV dexamethasone and PO dexamethasone will be provided.

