8.7 Topline Analyses

Outputs covering the following topics will be included in the top-line analyses:

Study conduct:

- Relevant protocol deviations (Table and Listing)

Subject population:

- End of Treatment Summary
- Accrual by Region
- Accrual by stratification factors at randomization
- Demographic Characteristics Summary
- IVRS Stratification Factors Summary
- Baseline Myeloma Characteristics Summary (SI units)
- Other Baseline Laboratory Measurements Summary
- Baseline Myeloma (Cytogenetics and FISH) Risk Factors Summary
- Time from Diagnosis to Randomization Summary
- Baseline Physical Measurements Summary

Extent of exposure:

- Number of Cycles Summary

- Elotuzumab Dose Intensity Summary
- Dexamethasone Dose Intensity Summary
- Lenalidomide Dose Intensity Summary
- Elotuzumab Delay Summary
- Elotuzumab Omission Summary
- Elotuzumab Infusion Interruption Summary
- Lenalidomide Reduction Summary
- Lenalidomide Interruption Summary

Progression free survival:

- Currentness of Follow-Up for PFS (IRC, ITT definition) Summary
- PFS (IRC, Primary Def.) Analysis
- Kaplan-Meier plot of PFS (IRC, Primary Def.)
- PFS (IRC, Primary Def.) Analysis Adjusting for Different Baseline Covariates
- PFS (IRC, Primary def.) Hazard Ratio and 95% CI in Subsets (Forest plot)
- PFS (IRC, ITT Analysis)
- Kaplan-Meier plot of PFS (IRC, ITT)
- PFS (IRC, ITT) Analysis Adjusting for Different Baseline Covariates
- PFS (IRC,ITT) Hazard Ratio and 95% CI in Subsets (Forest plot)
- Kaplan-Meier plot of PFS (Inv., Primary Def.)
- Kaplan-Meier plot of PFS (Inv., ITT.)
- Concordance of PFS between the IRC and investigator
- Concordance and Timing of PFS per IRC and Investigator
- Assessment of Censoring Distributions with Reverse Kaplan Meier Plot of PFS (IRC, Primary Def.)
- Assessment of Censoring Distributions with Reverse Kaplan Meier Plot of PFS (IRC, ITT Def.)

Tumor response:

- Best Overall Response (IRC)
- Best Overall Response (Inv)
- Best Overall Response (IRC) Modified for Subsequent Therapy
- Best Overall Response (IRC) Odds Ratio and 95% CI in Subsets (Figure)
- Cross Tabulation of Modified Best Overall Response per IRC and Investigator
- Time to First Response (IRC) Summary
- Kaplan-Meier Plot of Duration of Response (IRC)

Overall survival (only when interim PFS and ORR analyses are positive):

- Currentness of Follow-Up for Overall Survival Summary Overall Survival Analysis
- Overall Survival Analysis Adjusting for Different Baseline Covariates

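### The computed lenalidomide interruption cannot register holds that touch Day 1 or Day 21 or cover a whole cycle, and the SAP does not say whether computed or reported interruptions are tabulated

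*SAP*

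**What the plan says.** SAP 7.4.1.2 (Lenalidomide, Dose Interruption) calls the dose in a cycle "interrupted if there is a gap of two or more days between two dosing dates within that cycle". On the data source it adds: "This will be calculated based on the information from the dose modification CRF for Lenalidomide".

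The output is the number and percentage of subjects with any interruption and with one, two, three, or four or more. That sentence ends "reported interruptions will be presented", whereas the next one reads: "For subjects with a computed interruption, their reason for interruption will be summarized from the dose modification CRF". The section therefore uses both terms and does not say which one is tabulated.

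Three other passages fix the calendar and the use of the result:

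- SAP 6.2 gives the schedule: "Lenalidomide: 25 mg po on Days 1-21 of each cycle".
- Protocol 4.3.3 says that "the start of each cycle cannot be delayed and is fixed relative to Cycle 1 Day 1", and that doses missed outside the allowed window are skipped.
- SAP 8.7 includes the "Lenalidomide Interruption Summary" among the topline outputs.

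Lenalidomide has no delay or omission category in SAP 7.4.1.2, although elotuzumab and IV dexamethasone have both. By-subject listings of all reported events are planned for elotuzumab delays and omissions and for lenalidomide reductions. None is stated for lenalidomide interruptions.

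**The concern.** The rule needs a dose before the gap and a dose after it, both in the same cycle. A hold in force on Day 1 has no earlier dose in that cycle. A hold that lasts through Day 21 has no later one, because Days 22-28 carry no planned dose. A wholly missed cycle has neither. Because the cycle start is fixed, a hold at Day 1 does not move the calendar so as to bring the gap inside a cycle.

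The table could therefore register a two-day gap in mid-cycle and not register a missed cycle. It is a topline description of how well lenalidomide, which both arms receive, could be delivered. If the computed count is the one used, a subject whose only holds are of these kinds appears as never interrupted and drops out of the reasons summary.

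**Working it through.** **Inputs.** Planned dosing on Days 1-21 of 28 (SAP 6.2); fixed cycle start and skipped doses (Protocol 4.3.3); a gap of at least two days between two dosing dates in one cycle (SAP 7.4.1.2).

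**The plan's own figure.** SAP 7.4.1.3 gives a planned lenalidomide intensity of 131.25 mg/week, or 52.5 mg/week for a 10 mg start. The schedule reproduces both: 25 × 21 / 4 = 131.25 and 10 × 21 / 4 = 52.5.

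**When a hold is counted.** Let s be the first missed day and L the length of the hold in calendar days, with L at least 2. A dose before the gap requires s ≥ 2. A dose after it in the same cycle requires s + L ≤ 21. The countable start days run from 2 to 21 − L, which is 20 − L days, and none when L ≥ 20. Reading the gap as days without drug or as a difference between dates gives the same counts for these holds.

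| Hold length L (days) | Counted, start Days 2-21 | Counted, start Days 1-21 | Counted if planned days are used, start Days 1-21 |
|---|---|---|---|
| 3 | 17/20 (85%) | 17/21 (81%) | 20/21 |
| 7 | 13/20 (65%) | 13/21 (62%) | 20/21 |
| 14 | 6/20 (30%) | 6/21 (29%) | 21/21 |
| 19 | 1/20 (5%) | 1/21 (5%) | 21/21 |
| 20, 21, 28 | 0 | 0 | 21/21 |

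The last column applies a rule of two or more consecutive planned doses missed, across cycle boundaries. The single start day not counted for L = 3 and L = 7 is Day 21, where only one planned dose is missed.

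**Examples.** Take six cycles at 25 mg, so 126 planned doses over 168 days, with one hold that begins in Cycle 3. Relative dose intensity follows the SAP 7.4.1.3 formula.

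| Hold | Doses missed | Interruptions computed | Relative dose intensity |
|---|---|---|---|
| Days 8-14 | 7 | 1 | 119/126 = 94.4% |
| Days 1-7 | 7 | 0 | 119/126 = 94.4% |
| Days 15-28 | 7 | 0 | 119/126 = 94.4% |
| Whole cycle | 21 | 0 | 105/126 = 83.3% |
| Day 15 to Day 14 of the next cycle | 21 | 0 | 105/126 = 83.3% |

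If Cycles 5 and 6 are held and dosing never resumes, the computed count is 0 and relative dose intensity stays at 100%. The denominator stops 28 days after the first dose of the last cycle with lenalidomide: 84 × 25 / 16 weeks = 131.25 mg/week.

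**The case against.** Several points on the other side have force.

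- **Computed or reported.** A reader might infer that these holds are never counted in the table. The documents do not settle that. The source is the dose modification CRF and the frequency line says reported, so a table of CRF-reported holds could include them. This does not clear the plan: the section also says that the interruption is calculated, the reasons line says computed, and the elotuzumab text uses reported for delays that it has just defined by computation.
- **How often it happens.** A reader might infer from the blood-count schedule (Days 1 and 15 in Cycles 3-18, Day 1 only from Cycle 19), together with "Interrupt lenalidomide treatment; follow complete blood counts weekly" in Protocol 4.3.4.3, that the uncounted holds are the usual ones. A hold from Day 15 resumed on Day 22 is indeed uncounted (15 + 7 = 22 > 21). But Protocol Table 5.1-3 allows blood to be drawn up to 3 days before the visit, and a hold from Day 12 to a recheck on Day 19 is counted (12 + 7 = 19). Cycles 1-2 have weekly counts, and a hold from Day 8 resumed on Day 15 is counted. Protocol 4.3.3.3 also leaves delays to the investigator's discretion. No document gives the distribution of hold timing.
- **Between-arm effect.** A reader might infer that a difference between arms is understated. That is not shown. The table is per subject, so one detected hold is enough to enter the row for any interruption, and the direction depends on how hold timing and length differ by arm.
- **Other outputs.** Lenalidomide dose intensity is also topline, and it falls when a hold is followed by resumed dosing. It gives no event counts or reasons, and it does not reflect a hold with no resumption.
- **Purpose of the restriction.** Staying within a cycle keeps the planned rest week from being read as a gap. That aim is sound, but it can be met without losing the holds at either end.

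**Conclusion.** The point stands as a defect in a stated rule. As computed, a lenalidomide hold in place on Day 1, running through Day 21 or covering a whole cycle is not counted, and neither is any single hold of 20 or more days. Those results follow from the definition, the Day 1-21 schedule and the fixed cycle start, with no assumption about timing. Holds of that length are not remote: Protocol 4.3.3 contemplates delays in study treatment of 28 and up to 42 days. The fractions 13/20 and 6/20 assume a uniform first missed day over Days 2-21 and are illustrative only.

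The consequence is limited to a descriptive topline table and its reasons summary, where reasons are lost for certain only for subjects with no detected hold. PFS, ORR and OS are untouched. The documents do not support a claim that the affected holds are the typical ones, or that a between-arm difference is biased in a known direction. The unclear choice between reported and computed interruptions needs resolving in the same amendment.

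**What to change.** In SAP 7.4.1.2:

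1. Define a lenalidomide interruption as two or more consecutive planned dosing days (Days 1-21 of each cycle, anchored to Cycle 1 Day 1) without lenalidomide, from the first lenalidomide dose to lenalidomide discontinuation. Include gaps at the start or end of a cycle and gaps over whole cycles.
2. Leave the planned rest week out of the day count, and treat a gap that spans it as one episode.
3. For subjects on the every-48-hours regimen, count only that regimen's planned dosing days.
4. State that the frequency table and the reasons summary use this computed count.
5. Add a by-subject listing of all CRF-reported lenalidomide interruptions, whether or not they meet the computed definition, as is already planned for elotuzumab delays and lenalidomide reductions.

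The cost is a wording change, one reprogrammed variable and one listing. The SAP already derives lenalidomide reductions from daily doses on the study medication eCRF page, so no new data collection appears to be needed. The reported interruption frequency will be higher than under the present computed rule.
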